#### **4.11.2. Laboratory Data**

The following values will be summarized for each hematology and clinical chemistry laboratory parameter by treatment group:

1. Baseline (Screening) - Observed
2. Week 12 - Observed and change from Baseline
3. EOS - Observed and change from Baseline

In the event of repeat values, the last non-missing value per study visit will be used.

All laboratory data, including Common Terminology Criteria for Adverse Events (CTCAE) 4.03 grade, will be provided in data listings. See [Section 7.3](#) for CTCAE grade definitions.

#### **4.11.3. Vital Signs and Physical Examinations and Index Hip Assessment**

The actual value and change from Baseline (Day 1) at each time point will be summarized by treatment group. Vital sign measurements will be presented for each patient in a data listing.

All physical examination results will be presented in a data listing.

---

The incidence of inflammation, as determined from the index hip assessment, will be tabulated for each visit by treatment group. For those patients experiencing inflammation, the details of the inflammation will also be tabulated. In these tabulations, percentages will be based on those patients who have a non-missing index hip assessment at a given visit. Index hip assessment as well as index hip aspiration data will be presented in data listings.

#### **4.11.4. Index Hip X-Ray**

Index hip X-rays are performed at Screening and Week 12 for all patients and EOS for all some patients depending on the timing of the EOS visit. All X-rays will be read centrally. At Screening, each patient will have at least one X-ray reading. If the patient is found ineligible by the first reader, they will receive a second eligibility reading. Follow-up visits will have two independent safety readings and findings for osteonecrosis and subchondral insufficiency fracture will be adjudicated by a third reader.

The Screening X-ray will include the following variables:

- K-L grade (0-4)
- Osteonecrosis (absent/present)
- Subchondral insufficiency fracture (absent/present)
- Joint Space Narrowing (JSN) (0-3)
- Sclerosis (absent/present)
- Attrition (absent/present)

The Week 12 and EOS X-rays will include the following variables:

- Osteonecrosis (absent/present)
- Subchondral insufficiency fracture (absent/present)
- Joint Space Narrowing (JSN) (0-3)
- Sclerosis (absent/present)
- Attrition (absent/present)

The variables will be analyzed and presented as follows:

##### K-L Grade

K-L grade at Screening will be summarized and presented with the OA history and index hip characteristics data. If there is more than one eligibility reading, the second will be used for analysis.

##### Osteonecrosis and Subchondral Insufficiency Fracture

Osteonecrosis and subchondral insufficiency fracture will each be measured on a binary scale as absent or present (0=absent, 1=present). For the Screening X-ray, if there is more than one eligibility reading, the second will be used for analysis. Follow-up X-rays will be adjudicated as follows:

- 
- If Reader 1 and Reader 2 agree (are concordant) on the score of absent or present, then that score is used in the analysis.
  - If Reader 1 and Reader 2 do not agree (are discordant) on the score of absent or present, then the X-ray will be read by a third independent radiologist and scored as absent or present. The adjudicated score will agree with either Reader 1 or Reader 2 and that score will be used in the analysis.

### JSN

JSN will be scored according to the following 4-point ordinal scale of 0 to 3 scale:

0. None: Normal appearance.
1. Mild: Presence of mild narrowing.
2. Moderate: Presence of moderate narrowing.
3. Severe: Presence of severe narrowing.

JSN will be defined as follows:

- If Reader 1 and Reader 2 agree (are concordant) on the JSN score, then that score will be used in the analysis.
- If Reader 1 and Reader 2 do not agree (are discordant) then the average score of Reader 1 and Reader 2 will be obtained and used in the analysis.

### Sclerosis and Attrition

Sclerosis and attrition will each be measured on a binary scale as absent or present (0=absent, 1=present) by each reader.

Sclerosis and attrition will each be defined as follows:

- If Reader 1 and Reader 2 agree (are concordant), then that score will be used in the analysis.
- If Reader 1 and Reader 2 do not agree (are discordant) a score of 0 (absent) will be used in the analysis.

Change from Baseline to Week 12 and change from baseline to EOS (where available) in JSN score will be presented by treatment group. Any patients whose serial X-rays demonstrate a  $\geq 1$ -point grade increase in JSN will be categorized as indicating Chondrolysis. The frequency and percentage of Chondrolysis will be presented in a summary table.

Shift tables of osteonecrosis, subchondral insufficiency fracture, JSN, sclerosis and attrition will be presented by treatment group.

These X-ray data for all patients, including results for each reader, will be presented in a by patient listing. A separate listing will present Baseline K-L grade.

---

After review of X-ray results additional sensitivity analyses may be performed to better understand imaging results.

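### Sclerosis and attrition usually rest on one X-ray read at Screening but need two concordant reads at follow-up, so reader disagreement alone can appear as resolution in the shift table

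*SAP*

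**What the plan says.** SAP 4.11.4 (Index Hip X-Ray) provides at least one central read at Screening. A second is made only in one case: "If the patient is found ineligible by the first reader, they will receive a second eligibility reading". Week 12 and end-of-study films each get two independent reads.

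Disagreement between the two follow-up readers is handled in three ways:

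- Osteonecrosis and subchondral insufficiency fracture: "then the X-ray will be read by a third independent radiologist and scored as absent or present".
- Joint space narrowing (JSN): "then the average score of Reader 1 and Reader 2 will be obtained and used in the analysis".
- Sclerosis and attrition: "If Reader 1 and Reader 2 do not agree (are discordant) a score of 0 (absent) will be used in the analysis".

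A rise of at least one point matters for JSN, because any such "grade increase in JSN will be categorized as indicating Chondrolysis". Shift tables by treatment group are planned for all of these items. Each reader's result goes into a by-patient listing, but SAP 7.1 lists no reader-level table. Beyond that the SAP says only: "After review of X-ray results additional sensitivity analyses may be performed to better understand imaging results".

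Where there are two eligibility reads, the second is used for K-L grade ("If there is more than one eligibility reading, the second will be used for analysis") and for osteonecrosis and fracture ("For the Screening X-ray, if there is more than one eligibility reading, the second will be used for analysis"). The JSN, sclerosis and attrition paragraphs contain no such sentence.

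**The concern.** The two sides of the shift table are measured by different rules. At Screening, one reader is usually enough to record sclerosis. At follow-up, both readers must see it. A hip that has not changed, read as present at Screening and then as present by one reader and absent by the other, is tabulated as going from present to absent. Conversely, a genuinely new finding that only one follow-up reader sees is not recorded in the analysis value.

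The exposure for sclerosis is not remote. Eligible hips are K-L grade 2 or 3 (Protocol 7.4.2), and Protocol 7.9.6 describes those grades with slight and moderate sclerosis. Many hips may therefore start as present.

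Joint structure is a local safety question for a steroid injected into the hip. What is at stake is that disagreement between readers is taken for improvement, and that findings by one reader are visible only in a listing.

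**Working it through.** The plan states no reader accuracy or agreement figures, so there is no figure of its own to reproduce. The direction follows from the rules; the size needs assumptions.

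**Sclerosis in a truly sclerotic, unchanged hip.** Let q be the chance that one reader scores sclerosis present, assumed 0.7 to 0.9, and c the correlation between reads, assumed 0 to 0.5 and equal for all three reads.

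- Spurious resolved: Screening present, follow-up not present by both.
- Spurious new: Screening absent, follow-up present by both.

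With c = 0, resolved = q(1 − q²) and new = (1 − q)q². With c = 0.5, a beta-binomial model with a = q(1 − c)/c = q and b = (1 − q)(1 − c)/c = 1 − q gives resolved = q[1 − (q + 1)(q + 2)/6] and new = (1 − q)q(q + 1)/6.

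| q | c | Resolved | New | Ratio |
|---|---|---|---|---|
| 0.7 | 0 | 0.7 × 0.51 = 35.7% | 0.3 × 0.49 = 14.7% | 2.4 |
| 0.8 | 0 | 0.8 × 0.36 = 28.8% | 0.2 × 0.64 = 12.8% | 2.3 |
| 0.9 | 0 | 0.9 × 0.19 = 17.1% | 0.1 × 0.81 = 8.1% | 2.1 |
| 0.7 | 0.5 | 0.7 × 0.235 = 16.5% | 0.357/6 = 6.0% | 2.8 |
| 0.8 | 0.5 | 0.8 × 0.160 = 12.8% | 0.288/6 = 4.8% | 2.7 |
| 0.9 | 0.5 | 0.9 × 0.0817 = 7.4% | 0.171/6 = 2.9% | 2.6 |

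For independent reads the ratio is (1 + q)/q, which is above 2 for any q. The imbalance comes from the unequal number of reads. With one read at each visit, both kinds of spurious shift would have probability q(1 − q): 21%, 16% and 9% for q = 0.7, 0.8 and 0.9.

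**Patients.** SAP 4.1 plans about 35 per arm. Assume 20 to 35 of them truly have sclerosis and all have a Week 12 film.

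- Resolved: from 20 × 0.0735 = 1.5 to 35 × 0.357 = 12.5 per arm.
- New: from 20 × 0.0285 = 0.6 to 35 × 0.147 = 5.1 per arm.

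**JSN.** Take a whole-grade Screening value b. If one follow-up reader scores b + 1 and the other b or lower, the average change is at most +0.5. All 12 such patterns on the 0 to 3 scale (2 for b = 0, 4 for b = 1, 6 for b = 2) miss the one-point threshold. The +0.5 still enters the JSN change table. Two reads of at least b + 1 imply an average of at least b + 1, which implies at least one read of at least b + 1. The written chondrolysis count therefore always lies between a both-readers count and an at-least-one-reader count.

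**Two eligibility reads.** The missing sentence can change a result. With JSN reads of 2 then 1 at Screening and 2 and 2 at follow-up, using the second read gives +1.0 (chondrolysis) and averaging gives +0.5 (not). With sclerosis absent then present at Screening and present by both at follow-up, the second read gives no change and the discordance rule gives a new finding.

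**The case against.** Requiring two readers for a finding is a legitimate primary rule. An either-reader rule multiplies false positives: at an assumed 5% per reader with independent reads, 1 − 0.95² = 9.75% against 0.05² = 0.25%. A reader might infer that the SAP should switch to an either-reader definition or adjudicate everything. Nothing in the documents supports calling the written rule wrong, and this point does not ask for its replacement.

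Averaging JSN is a conventional choice, and the half-grade change stays visible. Each reader's result is already listed for about 70 patients. SAP 2.4 makes all Part I endpoints exploratory, and Protocol 9.4 gives Part II its own SAP. All of this stands, and it is why the point is minor. The listing does not summarise the disagreement, though, and optional analyses chosen once the X-ray results are known are weaker than rows fixed beforehand.

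On two eligibility reads, the Reader 1 and Reader 2 wording most naturally describes follow-up, because that is how the osteonecrosis paragraph uses it. The gap concerns only patients whom the first reader found ineligible but who were still enrolled. These should be few, although their number is not given. It is a clarification and would not merit a comment alone.

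Nothing comparable can be said about the size for attrition. The K-L grade 2 and 3 descriptions do not mention it, and how slight sclerosis maps to absent or present depends on reading instructions that are not in the documents.

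**Conclusion.** The point holds as a minor one. The unequal number of reads lets disagreement alone appear as resolved sclerosis or attrition, keeps single-reader new findings out of the analysis value, and keeps single-reader one-grade JSN rises out of the chondrolysis count. Under the assumptions above, spurious resolution of sclerosis affects about 7% to 36% of truly sclerotic, unchanged hips and spurious new sclerosis about 3% to 15%. That is roughly 1.5 to 12.5 and 0.6 to 5 patients per arm. The direction follows from the rules; the sizes rest on assumed sensitivity, correlation and prevalence.

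Three stronger readings are tempting and not supported:

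- **That apparent resolution has almost no counterpart among new findings.** A single Screening read can also miss sclerosis that both follow-up readers then see, so the imbalance is about 2.1 to 2.8 to 1.
- **That the highest resolution rate applies to a whole arm.** The 51% chance (1 − 0.7²) is conditional on Screening present. At q = 0.7 only about 35 × 0.7 = 24.5 hips would be scored present, and 24.5 × 0.51 = 12.5.
- **That the rule favours FX006.** It is the same in both arms and should affect them alike if the central readers do not know the treatment. The distortion is mainly in within-arm shifts.

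**What to change.** Keep every written derivation in SAP 4.11.4 and add three things.

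1. **One table, labelled supplementary**, by treatment group at Week 12 and at end of study where available, with the number at risk for each row:
   - chondrolysis by both readers, by the written average rule, and by at least one reader;
   - new sclerosis and new attrition by both readers (the written rule) and by at least one;
   - resolved sclerosis and resolved attrition as absent by both readers, and as absent by at least one (the written rule).
2. **A footnote to the shift table** saying that shifts in either direction can arise from reader error, and that setting one Screening read against two follow-up reads favours present-to-absent shifts.
3. **A clarifying sentence** that, where there are two eligibility reads, the second is also the Screening value for JSN, sclerosis and attrition, as already written for K-L grade, osteonecrosis and fracture.

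No new reads are needed, because the reader-level results are already to be listed. The costs are more false positives in the either-reader rows for new findings, which is why the table must stay supplementary, and sparse cells. Few hips may be at risk of new sclerosis. End-of-study rows may be thin because that visit is not required for Part I patients discontinued at the amendment (Protocol Table 7-3, footnote p).

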#### **4.11.5. Concomitant Medications**

Concomitant medications will be defined as those medications that were initiated after study drug administration or those that were ongoing at the time of study drug administration. If the start date or stop date of a medication is partially missing, the date will be compared as far as possible with the date of the start of administration of study drug. The medication will be assumed to be prior medication if it cannot be definitively shown that the medication did not start or continue after study drug administration and was not ongoing at the time of study drug administration. The following approach will be taken:

- If the start date of medication is complete and occurs on or after the day of administration of study treatment, the medication will be assumed concomitant. If the start date occurs prior to administration of study treatment but the end date is on or after the administration of study treatment date or the medication is recorded as ongoing, the medication will be considered concomitant.
- If the start day is missing but the start month and year are complete, a medication will only be excluded as being concomitant if the start month/year is before the month/year of study drug administration and if the stop date (either full date, month and year if missing day, or year if missing month and day) is before study drug administration.
- If the start day and month are missing but the start year is complete, a medication will only be excluded as concomitant if the start year is before the year of study drug administration and if the stop date (either full date, month and year if missing day, or year if missing month and day) is before study drug administration.
- If the start date is completely missing and the stop date is prior to administration of study treatment or completely missing, the medication will be assumed to be a prior medication.

All prior and concomitant medications (CM) will be presented in a data listing with flags indicating whether each medication was prior and/or concomitant. The listings will include type of medication (general or restrictive) and whether the CM was used for treatment of an AE.

#### **4.11.6. Surgical Procedures**

Surgical procedures that occurred during the study will be provided in a data listing.

---

## 5. CHANGES TO PLANNED ANALYSES

There are no major changes to the planned analyses.

The following minor changes were made:

1. As a result of the six patients who were unable to receive complete study drug administration, the analysis populations were updated as follows:
  - a. The FAS was updated to clarify that this includes only patients who received a full dose of study drug ([Section 3.1](#)).
  - b. The SP was updated to clarify that this includes all patients who received at least one dose (full or partial) of study drug ([Section 3.1](#)).
2. Study site was added as a covariate, since it was determined in previous studies to be an important covariate ([Section 4.2.4](#)).
3. The protocol indicates that categorical end points will be compared via chi-square or exact tests. Instead, logistic regression will be used to analyze the WOMAC A pain ([Section 4.10.1.3](#)), PGIC categorical ([Section 4.10.2.2](#)) and OMERACT responder ([Section 4.10.3](#)) outcomes. This allows us to control for covariates in the models.

---

## 7. CLINICAL STUDY REPORT APPENDICES

### 7.1. Statistical Tables and Figures to be Generated

Table 14.1.1	Patient Enrollment and Disposition
Table 14.1.2	Demographic and Baseline Characteristics (Safety Population)
Table 14.1.3	Osteoarthritis History and Index Hip Characteristics (Safety Population)
Table 14.1.4	Summary of Major Protocol Deviations (Safety Population)
Table 14.1.5	Study Drug Exposure Summary (Safety Population)
Table 14.2.1.1	Analysis of WOMAC A Pain Subscale (Full Analysis Set)
Figure 14.2.1.1	LS Mean Change from Baseline (+/- SE) in WOMAC A Pain Subscale Over Time (Full Analysis Set)
Table 14.2.1.1.1	Analysis of WOMAC A Pain Subscale, Patients with Baseline WOMAC A Pain Score 5 to <6 (Full Analysis Set)
Table 14.2.1.1.2	Analysis of WOMAC A Pain Subscale, Patients with Baseline WOMAC A Pain Score 6 to <7 (Full Analysis Set)
Table 14.2.1.1.3	Analysis of WOMAC A Pain Subscale, Patients with Baseline WOMAC A Pain Score $\geq 7$ to 9 (Full Analysis Set)
Figure 14.2.1.1.1	LS Mean Change from Baseline (+/- SE) in WOMAC A Pain Subscale Over Time by Baseline WOMAC A Pain Score (Full Analysis Set)
Table 14.2.1.1.2.1	Analysis of WOMAC A Pain Subscale, Patients with Unilateral Hip OA (Full Analysis Set)
Table 14.2.1.1.2.2	Analysis of WOMAC A Pain Subscale, Patients with Bilateral Hip OA (Full Analysis Set)
Figure 14.2.1.1.2	LS Mean Change from Baseline (+/- SE) in WOMAC A Pain Subscale Over Time by Unilateral/Bilateral Hip OA (Full Analysis Set)
Table 14.2.1.2	Analysis of WOMAC B Stiffness Subscale (Full Analysis Set)
Figure 14.2.1.2	LS Mean Change from Baseline (+/- SE) in WOMAC B Stiffness Subscale Over Time (Full Analysis Set)
Table 14.2.1.2.1.1	Analysis of WOMAC B Stiffness Subscale, Patients with Baseline WOMAC A Pain Score 5 to <6 (Full Analysis Set)

---

Table 14.2.1.2.1.2	Analysis of WOMAC B Stiffness Subscale, Patients with Baseline WOMAC A Pain Score 6 to <7 (Full Analysis Set)
Table 14.2.1.2.1.3	Analysis of WOMAC B Stiffness Subscale, Patients with Baseline WOMAC A Pain Score $\geq 7$ to 9 (Full Analysis Set)
Figure 14.2.1.2.1	LS Mean Change from Baseline (+/- SE) in WOMAC B Stiffness Subscale Over Time by Baseline WOMAC A Pain Score (Full Analysis Set)
Table 14.2.1.2.2.1	Analysis of WOMAC B Stiffness Subscale, Patients with Unilateral Hip OA (Full Analysis Set)
Table 14.2.1.2.2.2	Analysis of WOMAC B Stiffness Subscale, Patients with Bilateral Hip OA (Full Analysis Set)
Figure 14.2.1.2.2	LS Mean Change from Baseline (+/- SE) in WOMAC B Stiffness Subscale Over Time by Unilateral/Bilateral Hip OA (Full Analysis Set)
Table 14.2.1.3	Analysis of WOMAC C Function Subscale (Full Analysis Set)
Figure 14.2.1.3	LS Mean Change from Baseline (+/- SE) in WOMAC C Function Subscale Over Time (Full Analysis Set)
Table 14.2.1.3.1.1	Analysis of WOMAC C Function Subscale, Patients with Baseline WOMAC A Pain Score 5 to <6 (Full Analysis Set)
Table 14.2.1.3.1.2	Analysis of WOMAC C Function Subscale, Patients with Baseline WOMAC A Pain Score 6 to <7 (Full Analysis Set)
Table 14.2.1.3.1.3	Analysis of WOMAC C Function Subscale, Patients with Baseline WOMAC A Pain Score $\geq 7$ to 9 (Full Analysis Set)
Figure 14.2.1.3.1	LS Mean Change from Baseline (+/- SE) in WOMAC C Function Subscale Over Time by Baseline WOMAC A Pain Score (Full Analysis Set)
Table 14.2.1.3.2.1	Analysis of WOMAC C Function Subscale, Patients with Unilateral Hip OA (Full Analysis Set)
Table 14.2.1.3.2.2	Analysis of WOMAC C Function Subscale, Patients with Bilateral Hip OA (Full Analysis Set)
Figure 14.2.1.3.2	LS Mean Change from Baseline (+/- SE) in WOMAC C Function Subscale Over Time by Unilateral/Bilateral Hip OA (Full Analysis Set)
Table 14.2.4.1	Analysis of WOMAC Total (Full Analysis Set)

---

---

Figure 14.2.4.1	LS Mean Change from Baseline (+/- SE) in WOMAC Total Over Time (Full Analysis Set)
Table 14.2.1.5.1	Analysis of Area Under the Effect Curve (AUE), WOMAC A Pain Subscale Change from Baseline (Full Analysis Set)
Table 14.2.1.5.2	Analysis of Area Under the Effect Curve (AUE), WOMAC C Function Subscale Change from Baseline (Full Analysis Set)
Table 14.2.1.6	Analysis of WOMAC A Responders (Full Analysis Set)
Figure 14.2.1.6.1	Proportion of Responders, $\geq 20\%$ Improvement (Full Analysis Set)
Figure 14.2.1.6.2	Proportion of Responders, $\geq 30\%$ Improvement (Full Analysis Set)
Figure 14.2.1.6.3	Proportion of Responders, $\geq 50\%$ Improvement (Full Analysis Set)
Figure 14.2.1.6.4	Continuous Responder Curve at Week 12 (Full Analysis Set)
Table 14.2.2.1	Analysis of Patient Global Impression of Change (PGIC) (Full Analysis Set)
Figure 14.2.2.1	LS Mean Change from Baseline (+/- SE) Patient Global Impression of Change (PGIC) Over Time (Full Analysis Set)
Table 14.2.2.1.1.1	Analysis of Patient Global Impression of Change (PGIC), Patients with Baseline WOMAC A Pain Score 5 to $< 6$ (Full Analysis Set)
Table 14.2.2.1.1.2	Analysis of Patient Global Impression of Change (PGIC), Patients with Baseline WOMAC A Pain Score 6 to $< 7$ (Full Analysis Set)
Table 14.2.2.1.1.3	Analysis of Patient Global Impression of Change (PGIC), Patients with Baseline WOMAC A Pain Score $\geq 7$ to 9 (Full Analysis Set)
Figure 14.2.2.1.1	LS Mean Change from Baseline (+/- SE) in Patient Global Impression of Change (PGIC) Over Time by Baseline WOMAC A Pain Score (Full Analysis Set)
Table 14.2.2.1.2.1	Analysis of Patient Global Impression of Change (PGIC), Patients with Unilateral Hip OA (Full Analysis Set)
Table 14.2.2.1.2.2	Analysis of Patient Global Impression of Change (PGIC), Patients with Bilateral Hip OA (Full Analysis Set)
Figure 14.2.2.1.2	LS Mean Change from Baseline (+/- SE) Patient Global Impression of Change (PGIC) by Unilateral/Bilateral Hip OA Over Time (Full Analysis Set)

---

---

Table 14.2.2.2	Analysis of Patient Global Impression of Change (PGIC) Results by Category (Full Analysis Set)
Figure 14.2.2.2	Patient Global Impression of Change (PGIC) Results by Category (Full Analysis Set)
Table 14.2.2.2.1.1	Analysis of Patient Global Impression of Change (PGIC) Results by Category, Patients with Baseline WOMAC A Pain Score 5 to <6 (Full Analysis Set)
Table 14.2.2.2.1.2	Analysis of Patient Global Impression of Change (PGIC) Results by Category, Patients with Baseline WOMAC A Pain Score 6 to <7 (Full Analysis Set)
Table 14.2.2.2.1.3	Analysis of Patient Global Impression of Change (PGIC) Results by Category, Patients with Baseline WOMAC A Pain Score $\geq 7$ to 9 (Full Analysis Set)
Figure 14.2.2.2.1	Patient Global Impression of Change (PGIC) Results by Category Baseline WOMAC A Pain Score (Full Analysis Set)
Table 14.2.2.2.2.1	Analysis of Patient Global Impression of Change (PGIC) Results by Category, Patients with Unilateral Hip OA (Full Analysis Set)
Table 14.2.2.2.2.2	Analysis of Patient Global Impression of Change (PGIC) Results by Category, Patients with Bilateral Hip OA (Full Analysis Set)
Figure 14.2.2.2.2	Patient Global Impression of Change (PGIC) Results by Category by Unilateral/Bilateral Hip OA (Full Analysis Set)
Table 14.2.3	Analysis of OMERACT-OARSI Responders (Full Analysis Set)
Figure 14.2.3.1.1	Proportion of OMERACT-OARSI Responders (Full Analysis Set)
Figure 14.2.3.1.2	Continuous OMERACT-OARSI Responder Curve at Week 12 (Full Analysis Set)
Table 14.2.4	Summary of Rescue Medication Usage (Full Analysis Set)
Figure 14.2.4	LS Mean (+/- SE) Average Rescue Medication Usage Over Time (Full Analysis Set)
Table 14.2.5.	Analysis of Sleep Interference (Full Analysis Set)
Figure 14.2.5	LS Mean Change from Baseline (+/- SE) in Sleep Interference Over Time (Full Analysis Set)
Table 14.2.6.1	Analysis of EQ-5D Mobility Dimension (Full Analysis Set)

---

---

Figure 14.2.6.1	LS Mean Change from Baseline (+/- SE) in EQ-5D Mobility Dimension Over Time (Full Analysis Set)
Table 14.2.6.2	Analysis of EQ-5D Self-Care Dimension (Full Analysis Set)
Figure 14.2.6.2	LS Mean Change from Baseline (+/- SE) in EQ-5D Self-Care Dimension Over Time (Full Analysis Set)
Table 14.2.6.3	Analysis of EQ-5D Usual Activities Dimension (Full Analysis Set)
Figure 14.2.6.3	LS Mean Change from Baseline (+/- SE) in EQ-5D Usual Activities Dimension Over Time (Full Analysis Set)
Table 14.2.6.4	Analysis of EQ-5D Pain/Discomfort Dimension (Full Analysis Set)
Figure 14.2.6.4	LS Mean Change from Baseline (+/- SE) in EQ-5D Pain/Discomfort Dimension Over Time (Full Analysis Set)
Table 14.2.6.5	Analysis of EQ-5D Anxiety/Depression Dimension (Full Analysis Set)
Figure 14.2.6.5	LS Mean Change from Baseline (+/- SE) in EQ-5D Anxiety/Depression Dimension Over Time (Full Analysis Set)
Table 14.2.6.6	Analysis of EQ Visual Analogue Scale (EQ VAS) (Full Analysis Set)
Figure 14.2.6.6	LS Mean Change from Baseline (+/- SE) in EQ Visual Analogue Scale (EQ VAS) Over Time (Full Analysis Set)
Table 14.2.6.7	Analysis of EQ-5D-5L Index Score (Full Analysis Set)
Figure 14.2.6.7	LS Mean Change from Baseline (+/- SE) in EQ-5D-5L Index Score Over Time (Full Analysis Set)
Table 14.2.7	Analysis of HOOS-QOL Over Time (Full Analysis Set)
Figure 14.2.7	LS Mean Change from Baseline (+/- SE) in HOOS-QOL Over Time (Full Analysis Set)
Table 14.2.8.1	Analysis of TSQM-9 Global Satisfaction Domain at Week 12 (Full Analysis Set)
Table 14.2.8.2	Analysis of TSQM-9 Effectiveness Domain at Week 12 (Full Analysis Set)
Table 14.2.8.3	Analysis of TSQM-9 Convenience Domain at Week 12 (Full Analysis Set)

---

---

Table 14.3.1.1	Summary of Treatment-Emergent Adverse Events by Treatment Arm (Safety Population)
Table 14.3.1.2	Treatment-Emergent Adverse Events by System Organ Class and Preferred Term (Safety Population)
Table 14.3.1.3	Treatment-Emergent Adverse Events by Preferred Term (Safety Population)
Table 14.3.1.4	Treatment-Emergent Adverse Events by System Organ Class and Preferred Term - Related to Study Drug (Safety Population)
Table 14.3.1.5	Treatment-Emergent Adverse Events by System Organ Class and Preferred Term - Related to Injection Procedure (Safety Population)
Table 14.3.1.6	Treatment-Emergent Adverse Events by System Organ Class and Preferred Term by Maximum Severity (Safety Population)
Table 14.3.1.7	Treatment-Emergent Adverse Events by System Organ Class and Preferred Term – Leading to Study Discontinuation (Safety Population)
Table 14.3.1.8	Treatment-Emergent Adverse Events by System Organ Class and Preferred Term – Leading to Death (Safety Population)
Table 14.3.1.9	Serious Adverse Events by System Organ Class and Preferred Term (Safety Population)
Table 14.3.1.10	Index Hip-Related Treatment-Emergent Adverse Events by System Organ Class and Preferred Term (Safety Population)
Table 14.3.1.11	Index Hip-Related Treatment-Emergent Adverse Events by System Organ Class and Preferred Term - Related to Study Drug (Safety Population)
Table 14.3.1.12	Index Hip-Related Treatment-Emergent Adverse Events by System Organ Class and Preferred Term by Maximum Severity (Safety Population)
Table 14.3.2.1	Patient Listing of Deaths
Table 14.3.2.2	Patient Listing of Serious Adverse Events
Table 14.3.2.3	Patient Listing of Discontinuations Due to Adverse Events
Table 14.4.1.1	Summary and Change from Baseline for Hematology Parameters by Visit (Safety Population)

---

Table 14.4.1.2	Summary and Change from Baseline for Chemistry Parameters by Visit (Safety Population)
Table 14.4.1.3	Summary and Change from Baseline for Vital Signs (Safety Population)
Table 14.4.2	Summary of Index Hip Assessments (Safety Population)
Table 14.4.3.1	Index Hip X-ray Joint Space Narrowing Change from Baseline (Safety Population)
Table 14.4.3.2	Shifts in Index Hip X-Ray Assessments from Baseline (Safety Population)

